Protocol Title: Kardia – A smartphone-based care model for outpatient cardiac rehabilitation

Protocol No: Kardia

Principal Investigator: [name]

Protocol Version 1.1 dated 31 May 2017

Specific Aims and Hypothesis:

This study aims to show that a smartphone-based Cardiac rehabilitation program which provides blood pressure monitors and wearable vital signs monitors is feasible and safe in low risk post-myocardial infarction patients in Singapore.

The hypotheses are as follows:

1. Smart-phone based model for cardiac rehabilitation is safe and will improve adherence to recommendations for physical activity post-myocardial infarction
2. The uptake of this home cardiac rehabilitation would lead to improvement in the following objective outcome measures:
 - a. 6 minute walk tests
 - b. Cardiovascular risk factors
 - i. Blood pressure
 - ii. Blood tests, i.e. lipid profile, HbA1C
 - iii. Body weight/ Body Mass Index (BMI)/ Waist/hip circumference
 - iv. Smoking
 - c. Major Adverse Cardiovascular Events (MACE) and Hospitalizations (12 months)
3. This smart-phone based model will allow patients to play an active role in their own management resulting in improvement in lifestyle habits and quality of life
 - a. Physical activity
 - b. Dietary habits (Dietary Habits Questionnaire)
 - c. Psychosocial wellbeing (Kessler 10 Psychological Distress Scale; Depression, Anxiety and Stress Scale 21)
 - d. Quality of life (EQ5D)
 - e. Compliance to medications
 - f.
4. The program will result in a lasting change in patient behaviour and lifestyle.

Background and Clinical Significance

Cardiovascular disease (CVD) is the most common cause of death in Singapore, accounting for ~34% of deaths. This means 1 in every 3 deaths in Singapore is due to heart disease or stroke. Ischemic heart disease is the leading cause of mortality and accounts for 17% of all deaths attributable to life-style related risk-factors. The total burden of this disease is likely to increase given the aging population and the increase in prevalence of obesity and predisposing conditions such as diabetes mellitus, hypertension and hyperlipidaemia.

A number of modifiable environmental and patient specific factors increase the chance of developing coronary artery disease (1). These include smoking, high blood cholesterol, physical inactivity, diabetes, high blood pressure and obesity. Following myocardial infarction, acute coronary

syndromes, surgical and percutaneous interventions, cardiac rehabilitation has provided an avenue for reducing future cardiovascular risks in patients by positively influencing these factors (2-5). The eventual goal of the program is to engage patients with permanent behavioural and life-style changes. There is strong evidence for the effectiveness of cardiac rehabilitation which is given a Class 1 recommendation from the American/European Cardiology guidelines, particularly for post-myocardial infarction patients (6, 7). Several studies and meta-analyses have demonstrated a significant reduction in mortality and morbidity (2, 8, 9).

Despite the clear benefits of cardiac rehabilitation programs, the uptake of these programs has been poor due to various patient and system factors (10-13). Cardiac rehabilitation programs are traditionally carried out in hospitals and health centres under the direct personal supervision of mentoring clinicians. Patient barriers, such as time constraints and distance from treatment centres lead to poor uptake of programs among eligible patients. To overcome these barriers, home-based care models have been proposed as a viable alternative to hospital-based cardiac rehabilitation programs even in the 1980s (14). The current state of mobile phone communication and technology provides not only the capacity but an especially attractive media option to support home-based cardiac rehabilitation programs (15, 16).

[figure not shown]
This study aims to investigate a smartphone-based cardiac rehabilitation program for patients recovering from myocardial infarction. The program focuses on providing patient centric self-monitoring platform enabling patients to take control and be actively involved in their medical care. The program (“Kardia”) is a 6-week rehabilitation program enabling patients to track their blood pressure, physical activity and medicine compliance through a mobile application. Each patient in the intervention arm is provided with a blood pressure monitor and activity tracker. The data from these devices would be automatically synced by a mobile application and uploaded to a confidential web portal which is only accessible by physician care-givers. The application also provides educational content/tasks, appropriate reminders for taking medications and daily goals on activity targets set by the care provider. This would help to engage the patients to enable behavioural change and improve compliance to medication and activity recommendations.

In Changi General Hospital, the uptake of cardiac rehabilitation among eligible patients is less than 20%. This study hopes to target the remaining 80% of patients who have refused the traditional cardiac rehabilitation program. It will be the first time that a smartphone based home cardiac rehabilitation program would be offered in Singapore. If shown to be safe and feasible, “Kardia” will help to improve patient outcomes in short to medium term. In addition, it may empower the patients to take a more active role in their medical care and promote long lasting behavioural changes in the long term. There will also be a significant operation impact if “Kardia” can be rolled out as an alternative care model to the traditional centre-based cardiac rehabilitation program, enabling greater patient access to “cardiac rehabilitation”. This is also in line with national initiatives to promote an active and healthy lifestyle, i.e. National Steps Challenge by the Health Promotion Board.

Methods/Approach

The project is a randomized controlled study of smartphone based cardiac rehabilitation program compared to routine care in patients who did not sign up for traditional hospital-based cardiac rehabilitation. 50 patients who are randomized to the intervention group (mHealth) will be enabled with remote monitoring devices (Blood Pressure and wearable vital signs monitor, Biovotion) and “Kardia” mobile application, for home-based rehabilitation program followed by review in the outpatient Cardiology clinics. The control group (50 patients) will just be monitored at fixed intervals

in the outpatient Cardiology clinics. For drop out subjects, there will not be any subject replacement. See Figure below.

Cardiac Rehabilitation program

Patients will be advised to commence the exercise program 2 weeks after the myocardial infarction

Time	Exercise Intensity	Exercise Frequency/Duration	Patient actions
Week 1	light	3x/week; 10 minutes	Exercise diary
Week 2	light	3x/week; 20 minutes	
Week 3	light	3x/week; 30 minutes	
Week 4	moderate	3x/week; 15 minutes	
Week 5	moderate	3x/week; 30 minutes	
Week 6	moderate	4x/week; 30 minutes	
Week 7	moderate	5x/week; 30 minutes	
Week 8	moderate	5x/week; 30 minutes	

Inclusion criteria:

- Age 21-85 years
- Willing and able to provide informed consent
- New onset of Post ST elevation and non-ST elevation myocardial infarction/staged PCI/ acute coronary syndrome/unstable angina
- Own and able to operate App on smartphone

Exclusion criteria:

- History of ventricular fibrillation not in the setting of acute myocardial infarction
- Documented sustained ventricular or supraventricular arrhythmia
- Unstable angina
- Awaiting staged revascularization
- Inability to perform 6MWT

Block randomization using sequentially numbered sealed envelopes would be used to assign patients to the intervention or control arms.

The primary outcome measure is compliance and adherence to the “Kardia” program. Other endpoints include 6MWT, patient wellbeing and behaviour (e.g. dietary habits, stress levels, physical activity) assessed using questionnaires, major adverse cardiovascular events (MACE), modification of cardiovascular risk profiles (i.e. LDL, BP, BMI, HbA1c, etc) and medicine compliance. The outcome measures and the corresponding measurement tools are listed in Table 1.

Table 1.

Outcome Measures	Measurement Tools
Primary Outcome Measures:	
Compliance to smart phone based cardiac rehabilitation program	Uploading of completed data (BP, activity) to web portal (90% compliance in intervention group would be considered acceptable)
Adherence to physical activity guidelines (150 minutes of moderate level exercise per week) at months 3 and 9	Questionnaire (a difference of 30% is considered significant)
Secondary Outcome Measures:	
6MWT at baseline (within 2 weeks upon discharge) months 3 (+/- 2 months) and 9 (+/- 3 months)	6MWT
Risk Factors	Blood pressure Blood tests, i.e. lipid profile, HbA1C Body weight/ Body Mass Index (BMI)/ Waist/hip circumference Smoking
MACE or hospitalization	Clinical notes
Medication Compliance	Questionnaire
Overall well being	Questionnaire (EQ5D)
Dietary habits	Questionnaire (FFQ)
Psychosocial well being	Questionnaire (K10, DASS 21)
Additional analyses:	
Reasons for non-compliance	Questionnaire
Smoking status	Questionnaire (SMOKING CESSATION SERVICE QUESTIONNAIRE)
Satisfaction and Usability	Questionnaires for patients and clinical staff in intervention group
Costs	Cost to implement Kardia (Staff-time, project implementation, facility cost)
Predictive analyses for re-hospitalizations, etc	Biofourmis

Sample size calculation

Previous studies have shown compliance of centre-based cardiac rehabilitation programs at about 60%. Based on that assumption, a sample size of 50 patients is necessary to show a 30% improvement in compliance in the mHealth arm, with $\alpha=0.01$ and power of 90%.

Statistical analyses

Data will be expressed as mean \pm SD for continuous variables and medians and IQR for skewed data. Statistical comparisons will be performed using paired Student's t test for within group changes over time, unpaired Students' t test for differences between intervention and control arms. Wilcoxon signed-rank test will be used to compare skewed data. Categorical variables will be expressed as counts and percentages and will be analysed using Chi-square test (or Fisher's exact test). All statistical tests will be 2-tailed and statistical significance will be based on $p<0.05$

Data Collection

Paper case record forms will be prepared. Questionnaire booklets will be provided to obtain patient responses. A research assistant will record the data and the data will be checked by the principal investigator for quality assurance. The data will be entered into an electronic database which will be password protected.

Adverse Event and Serious Adverse Event Reporting

An adverse event (AE) is any untoward medical occurrence in a patient or clinical investigation subject administered investigational product and that does not necessarily have a causal relationship with this treatment. An AE can therefore be any unfavorable and unintended sign (including an abnormal laboratory finding), symptom, or disease temporally associated with the use of an investigational product, whether or not related to the investigational product.

A serious adverse event (SAE) or reaction is any untoward medical occurrence that:

- results in death
- is life-threatening
- requires inpatient hospitalisation or prolongation of existing hospitalisation
- results in persistent or significant disability/incapacity or
- is a congenital anomaly/birth defect
- is a medical event that may jeopardize the patient and may require medical or surgical intervention to prevent one of the outcomes listed above.

Neither of the two interventions is anticipated to lead to any major adverse events. Minor troubleshooting problems will be addressed as described above and recorded. In the event the clinical staff have concerns about patient's continuation of therapy or participation in the trial, the research staff will be notified. A discussion with the primary clinician will be conducted to facilitate further therapeutic decisions. As per good clinical practice, serious adverse events will be reported

promptly to the institution representative (local SAE resulting in death), sponsor or regulatory bodies as required and appropriate.

Reporting timeline to CIRB:

- SAE that result in death, regardless of causality, should be reported immediately - within 24 hours of the PI becoming aware of the event.
- Local life-threatening (unexpected/ expected) SAE should be reported no later than 7 calendar days after the Investigator is aware of the event, followed by a complete report within 8 additional calendar days.
- Local unexpected SAE that are related events, but not life-threatening, should be reported no later than 15 calendar days after the investigator is aware of the event.
- An increase in the rate of occurrence of local expected SAE, which is judged to be clinically important, should be reported within 15 calendar days after the PI is aware of the event.
- Local expected SAE should be reported annually (together with Study Status Report for annual review).
- Local unexpected and unlikely related SAE that are not life-threatening should also be reported annually (together with Study Status Report for annual review).
- Local unexpected AE that are related events should be reported at least annually (together with Study Status Report for annual review).
- Non-local unexpected SAE that are fatal or life threatening and definitely/probably/possibly related should be reported not later than 30 calendar days after the PI is aware of the event.

Protocol Deviations

The investigator should conduct the trial in compliance with the protocol. A protocol deviation is a planned or unplanned departure from the approved study protocol. Any deviation that significantly affects the safety and/or rights of a study subject or the integrity of the data must be recorded on a deviation form.

The following is a list of reasons a deviation form should be completed for this study:

- Subject was randomized and did not satisfy eligibility criteria
- Subject received the wrong product, contrary to the randomization scheme
- Changes in procedures not pre-approved by IRB (e.g., asking subjects to fast before signing consent, taking additional blood draw or measurement not outlined in protocol/consent, etc.)
- Others that may affect the rights and safety of a subject, including errors in the informed consent process
- Others as appropriate for the study

The following deviations do not need to be recorded on a deviation form because this information will be captured elsewhere in the study data and will be summarized in the final report:

- Missed procedure(s) or questionnaire(s)
- Missed or out of window study procedures
- Other(s) as determined by the study team during the course of the trial

Ethical considerations

This study will be conducted in accordance with the ethical principles that have their origin in the Declaration of Helsinki and that are consistent with the Good Clinical Practice and the applicable regulatory requirements.

This final study protocol, including the final version of the Patient Information and Informed Consent Form, must be approved in writing by the Centralised Institutional Review Board (CIRB), prior to enrolment of any patient into the study.

The principal investigator is responsible for informing the CIRB of any amendments to the protocol or other study-related documents, as per local requirement.

Retention of study documents

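### Smoking is labelled objective but measured by questionnaire, sits in two outcome tiers, and has no stated denominator or use of entry smoking status, which costs precision if all patients are compared

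*Combined protocol and SAP*

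**What the plan says.** Specific Aims and Hypothesis, hypothesis 2, states that uptake of the programme "would lead to improvement in the following objective outcome measures". Smoking is item b(iv), alongside blood pressure, blood tests and body measurements. Hypothesis 3 holds the lifestyle and quality-of-life items: physical activity, diet, psychosocial wellbeing, quality of life and medication compliance.

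Table 1 lists smoking twice:

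- Under secondary outcomes, the Risk Factors row ends "Body weight/ Body Mass Index (BMI)/ Waist/hip circumference Smoking". No instrument is given for smoking there.
- Under additional analyses, Smoking status is measured by "Questionnaire (SMOKING CESSATION SERVICE QUESTIONNAIRE)".

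Neither row gives a definition of smoking, a time point or a denominator. No biochemical check is described.

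Under Statistical analyses, the only rule that fits smoking is "Categorical variables will be expressed as counts and percentages and will be analysed using Chi-square test (or Fisher's exact test)". Also, "All statistical tests will be 2-tailed" and "statistical significance will be based on $p<0.05$".

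Under Methods/Approach, 50 patients are allocated to each arm by block randomisation with no stratification factor named. Smoking is not an entry criterion, so smokers and non-smokers are both randomised. Only the intervention arm receives the devices and the app.

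**The concern.** There are two separate problems.

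The first is status. A reader of hypothesis 2 expects smoking to be measured as blood pressure or HbA1c is. What Table 1 supports is self-report from patients who know whether they were given the programme. With smoking in two tiers, the plan does not settle whether a result is secondary or additional, and that choice could be made after the data are seen.

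The second is the analysis. A programme can help someone stop smoking only if they smoke. If the chi-square test compares smoking prevalence across everyone randomised, non-smokers dilute the effect. Chance differences between arms in the number of smokers at entry also add noise. The plan neither restricts the comparison nor adjusts for entry status, so a real cessation effect of moderate size is more likely to be missed, or to appear as no difference or the wrong direction, than it need be.

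**Working it through.** **No plan figure to reproduce.** The only sample size calculation concerns programme compliance. Nothing in the documents gives smoking prevalence, quit rates or power for smoking.

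**Inputs from the documents:** 50 per arm; two-sided 5% test; chi-square; no stratification.

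**Assumptions:** proportion smoking at entry p = 30%, 40% or 50%; quit rates, control v intervention, of 30% v 60% or 40% v 60%; no uptake among non-smokers; complete follow-up; chi-square without continuity correction. Fisher's test would give somewhat lower power under either denominator.

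**Step 1: size of the effect in all patients.** Follow-up smoking prevalence in an arm is p(1 − q), where q is the quit rate, so the difference between arms is p(q_i − q_c).

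- 30% v 60%: 0.30 × p = 9, 12, 15 points.
- 40% v 60%: 0.20 × p = 6, 8, 10 points.

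**Step 2: chance imbalance at entry and what remains of it.** The SD of the difference in entry smoking is √(2p(1 − p)/50) = 9.2, 9.8, 10.0 points. Some smokers quit, so the part carried to follow-up has SD √{p(1 − p)/50 × [(1 − q_c)² + (1 − q_i)²]}.

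Worked case, p = 0.4 and 30% v 60%:

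- Carried variance: 0.24/50 × (0.49 + 0.16) = 0.00312, SD 5.6 points.
- Total variance of the follow-up difference: (0.28 × 0.72 + 0.16 × 0.84)/50 = 0.00672, SD 8.2 points.
- Share due to entry imbalance: 0.00312/0.00672 = 46%.

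| Quit rates | p | Effect (points) | Carried SD (points) | Share of variance |
|---|---|---|---|---|
| 30% v 60% | 30% | 9 | 5.2 | 50% |
| | 40% | 12 | 5.6 | 46% |
| | 50% | 15 | 5.7 | 42% |
| 40% v 60% | 30% | 6 | 4.7 | 43% |
| | 40% | 8 | 5.0 | 39% |
| | 50% | 10 | 5.1 | 35% |

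**Step 3: power and direction, by simulation.** In each simulated trial, smokers at entry are binomial(50, p) in each arm and continuing smokers are binomial(entry smokers, 1 − q). The test is run on 50 v 50 and again on entry smokers only. With at least 200,000 trials per scenario:

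| Quit rates | p | Power, all | Power, entry smokers | Zero or wrong direction, all | Same, entry smokers |
|---|---|---|---|---|---|
| 30% v 60% | 30% | 24% | 39% | 14% | 5% |
| | 40% | 31% | 49% | 9% | 3% |
| | 50% | 39% | 58% | 6% | 2% |
| 40% v 60% | 30% | 14% | 20% | 24% | 15% |
| | 40% | 17% | 25% | 19% | 11% |
| | 50% | 21% | 30% | 15% | 8% |

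**Step 4: no true effect.** With equal quit rates of 40% in both arms, both tests reject in about 5% of trials.

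**Step 5: outside the main range.** At p = 20% and 40% v 60%, power is 10% in all patients and 15% in entry smokers. For a large effect, 40% v 80% with p = 30-50%, it is 48-73% and 63-84%.

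**The case against.** It can fairly be said that this is a labelling slip on one non-primary item, and that four stronger readings, which a reader might infer, go too far. All four do go too far.

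- *The plan commits to comparing all patients.* It does not. It states no denominator for smoking. The questionnaire's title suggests, without proving, that it is aimed at smokers. What stands is that the denominator and the handling of entry status are unspecified.
- *Chance differences in entry smoking overwhelm any cessation effect.* They do not. The SD at entry, 9-10 points, should not be set against an effect at follow-up. The carried SD is below the true effect in all six main scenarios, and entry imbalance explains about half of the variance at most. Only at 20% smokers with 40% v 60% does the carried SD (4.1 points) match the effect (4 points). The remaining noise comes from who happens to quit, and no choice of denominator removes it.
- *The comparison is biased.* In a randomised trial it is not, and step 4 shows type I error near 5%. The loss is in precision and interpretability.
- *The double listing is there to permit selective reporting.* Nothing in the documents shows this. The text leaves the choice open, and that is reason enough to close it.

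It can be added that the gain is moderate and a null result stays uninformative. That is also true, and it argues for reporting an estimate and for the word exploratory. It does not excuse leaving the tier, the label and the denominator unsettled.

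**Conclusion.** The point holds in a limited form. Calling smoking objective conflicts with the only tool named for it, and Table 1 assigns it to two tiers. Both are plain on the page and need no assumptions. The planned test is unadjusted, with no denominator stated and no use of entry smoking status.

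If the test is run on all patients, the price is lost power: roughly 15-19 percentage points for 30% v 60% quitting and 6-9 points for 40% v 60%. The chance of a zero or wrong-direction difference is also higher, at 6-14% against 2-5% and 15-24% against 8-15% respectively. These sizes rest on assumed smoking prevalence and quit rates and on complete follow-up. The direction was the same in every scenario with a true effect that was run. Neither primary outcome is affected, so this should be corrected but does not threaten the trial's main conclusions.

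**What to change.** - **Tier and label.** List smoking once in Table 1, as a self-reported secondary outcome. Remove it from the objective measures in hypothesis 2. Moving it to hypothesis 3, beside the other questionnaire-based behaviours, would be natural, but dropping the label is enough.
- **Definition.** State what counts as smoking at entry (before the index event or at enrolment), the recall period for follow-up smoking, the visits (for example months 3 and 9, which Table 1 already uses for physical activity and the walk test), and how missing answers are handled.
- **Analysis.** Compare self-reported smoking between randomised arms among patients who smoked at entry, or in all patients with adjustment for entry smoking status. Choose one in advance. Report the difference with a confidence interval and call it exploratory. Describe uptake among non-smokers.

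The cost is wording in the hypotheses, Table 1 and Statistical analyses, with no extra visits or patients. Entry smoking status must be recorded; the stated aim of modifying risk profiles implies that it is, but the documents do not say so. The restricted comparison has a smaller denominator, about 15-25 per arm (50 × 30% to 50 × 50%), and its power stays low.

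### The month-3 6MWT window opens at month 1, before the exercise programme ends, so mid-programme tests can enter the month-3 comparison (minor; one timepoint of one secondary outcome)

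*Combined protocol and SAP*

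**What the plan says.** Table 1 gives the timing of the walk test as "6MWT at baseline (within 2 weeks upon discharge) months 3 (+/- 2 months) and 9 (+/- 3 months". Read literally, the month-3 test may fall anywhere from month 1 to month 5, and the month-9 test from month 6 to month 12. The text does not say what the months are counted from.

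The section on the cardiac rehabilitation programme states "Patients will be advised to commence the exercise program 2 weeks after the myocardial infarction". Its table then runs for eight weeks. Exercise is light in weeks 1 to 3 and moderate from week 4, and the last two weeks are set at "5x/week; 30 minutes". The Background section describes a programme of 6 weeks instead.

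Methods/Approach says that intervention patients receive the devices and the app "for home-based rehabilitation program followed by review in the outpatient Cardiology clinics", and that controls "will just be monitored at fixed intervals". It refers to a figure ("See Figure below") that is not reproduced in the text available here.

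Hypothesis 2 reads "The uptake of this home cardiac rehabilitation would lead to improvement in the following objective outcome measures", and the 6MWT is the first measure listed under it. The Statistical analyses section plans a paired t test for change within an arm and an unpaired "t test for differences between intervention and control arms". Neither uses the date of the test. Under Protocol Deviations, out-of-window procedures need no deviation form and are summarised in the final report.

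**The concern.** Hypothesis 2 concerns what the programme achieves. A walk test taken part-way through the schedule measures partial exposure. A patient tested at the opening of the window, counted from infarction, would be in programme week 3 and would so far have been prescribed only light exercise. That result would enter the same month-3 comparison as one from a patient tested at month 5, well after the programme.

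Nothing in the plan separates the two. The early test is in window, so the out-of-window summary does not pick it up. Recorded visit dates could identify it, but no planned analysis uses them. What is at stake is how clearly the month-3 6MWT can be read as a post-programme result, with possible dilution of the difference between arms.

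**Working it through.** The plan states no figure to reproduce; the check is calendar arithmetic.

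**Inputs**
- Month-3 window: 3 − 2 = month 1 to 3 + 2 = month 5 (Table 1).
- Exercise start: day 14 after infarction (programme section).
- Programme length: 8 weeks (exercise table) or 6 weeks (Background).
- Arm size: 50 (Methods/Approach).
- Assumptions: 1 month = 365.25/12 = 30.44 days; a hospital stay of 1 week where discharge or baseline is the origin; and the visit patterns in step 4.

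**Step 1. Programme end.** 14 + 56 = day 70 (8 weeks); 14 + 42 = day 56 (6 weeks). Prescribed minutes per week by the table are 30, 60, 90 (light), then 45, 90, 120, 150, 150 (moderate). The 150-minute level is first prescribed in week 7, which begins on day 56.

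**Step 2. Window opening.** Opening day = origin + 30.4. Window length = 4 × 30.44 = 121.75 days.

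**Step 3. Share of the window's calendar time before programme end** = (end − opening) / 121.75.

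| Months counted from | Opens (day after infarction) | Before day 70 | Before day 56 |
|---|---|---|---|
| Infarction (day 0) | 30.4 | 39.6/121.75 = 32.5% | 25.6/121.75 = 21.0% |
| Discharge (assumed day 7) | 37.4 | 26.7% | 15.2% |
| Exercise start (day 14) | 44.4 | 21.0% | 9.5% |
| Latest baseline test (assumed day 7 + 14 = 21) | 51.4 | 15.2% | 3.7% |

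The window opens before the programme ends in every row and for both lengths. These are shares of time, not of patients.

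**Step 4. Share of tests.** This depends on when visits happen, which the documents do not give. Under assumed patterns within the window (origin infarction / exercise start), with the expected number out of 50 in brackets:

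| Visit pattern | Before day 70 | Before day 56 |
|---|---|---|
| Evenly spread | 32.5% / 21.0% (16 / 10.5) | 21.0% / 9.5% (10.5 / 4.8) |
| Triangular, peak at month 3 | 21.1% / 8.8% (10.6 / 4.4) | 8.8% / 1.8% (4.4 / 0.9) |
| Normal around month 3, SD 3 weeks | 15.4% / 4.5% (7.7 / 2.2) | 4.5% / 0.8% (2.2 / 0.4) |
| Normal, SD 2 weeks | 6.4% / 0.6% (3.2 / 0.3) | 0.6% / 0.0% (0.3 / 0) |
| Normal, SD 1 week | 0.1% / 0% (about 0) | 0% / 0% |

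**Step 5. Other timepoints.** A test at nominal month 3 (day 91.3) follows either programme end. The month-9 window opens at 6 × 30.44 = day 182.6, also after both.

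**Step 6. The proposed limit.** 91.3 − 14 = day 77.3, which is after day 70. It covers exercise starts up to 77.3 − 56 = day 21.3. Counted from infarction, the remaining window is 152.2 − 77.3 = 74.9 days, or 74.9/121.75 = 61% of the present length.

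**The case against.** The case for leaving the window alone has four parts.

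- A wide window is a sensible practical choice. There are 50 patients per arm with no replacement, they did not sign up for hospital rehabilitation, and the protocol names time and distance as barriers. A generous window limits missing tests. This stands for the upper side, which the fix keeps in full. It is weaker for the lower side, where the extra width is what admits mid-programme tests.
- Visits will probably cluster. Table 1 names month 3, and controls are to be seen at fixed intervals. This stands, and it is why the likely number affected is small.
- The same window applies to both randomised arms, so early tests do not by themselves invalidate the comparison. This also stands. Equal timing would still leave some intervention patients measured at partial exposure, but the documents give no 6MWT effect or SD from which to size any dilution.
- The plan never calls the month-3 test a post-programme test. That is correct: the intent is inferred from the order of events, the home programme first and clinic review after it. The figure not shown may also settle the time origin or the programme length.

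A reader might also infer that the primary adherence outcome at month 3 shares this fault. The documents do not support that: the window is written for the 6MWT only.

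**Conclusion.** The point holds, as a minor one. The month-3 6MWT window opens before the programme ends for each origin tested (infarction, exercise start, and discharge or baseline test with an assumed stay of up to 1 week) and for either stated programme length. The planned t tests would pool mid-programme and post-programme results.

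The number affected is probably small: about 0 to 3 of 50 intervention patients if visits keep to month 3 with an SD of 2 weeks or less. A reader might infer that about a third of month-3 tests would be taken mid-programme. That needs three things together: evenly spread visits, months counted from infarction, and the 8-week programme. The documents establish none of the three as a set, and the mention of fixed intervals points away from an even spread.

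Nor do the documents support a claim of bias in a known direction. Dilution is plausible, but its size and direction cannot be derived. The point touches one timepoint of one secondary outcome; month 9 and the primary outcomes are unaffected.

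**What to change.** Change only the lower limit in Table 1: month 3, −2 weeks / +2 months, counted in both arms from the index event. The month-3 6MWT is then scheduled no earlier than about day 77, and the upper limit stays at about day 152. Use one calendar limit for both arms, since controls may have no exercise start date.

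Keep any earlier test in the main analysis by randomised arm and flag it as out of window. Add a sensitivity analysis without the early tests. State that leaving them out is a post-randomisation exclusion, so that analysis is supportive only. The main result can therefore still contain some early tests; the gain is that fewer are scheduled and those that occur are visible.

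The cost is an amendment notified to the CIRB and one added sensitivity analysis, with no new visit and no discarded data. The window shortens from about 122 to 75 days, so more tests will be labelled out of window. The Protocol Deviations section already handles these without a deviation form.
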